## APPENDIX 1 – ECOG PERFORMANCE STATUS

### ECOG PERFORMANCE STATUS

Performance Status Criteria	
ECOG (Zubrod)	
Score	Description
0	Fully active; able to carry on all pre-disease performance without restriction
1	Restricted in physically strenuous activity but ambulatory and able to carry on normal activity; minor symptoms of disease
2	Ambulatory and capable of all self care but unable to carry out any work activities; up and about more than 50% of waking hours.
3	Capable of only limited self care; confined to bed or chair more than 50% of waking hours.
4	Completely disabled; cannot carry on any self care; totally confined to bed or chair.

## **APPENDIX 2 – CYP3A4 INHIBITORS, INDUCERS, AND SUBSTRATES**

### **CYP3A4 INHIBITORS, INDUCERS, AND SUBSTRATES**

The following list describes medications and foods which are common inhibitors, inducers, or substrates of CYP3A4. These medications should be used with caution during this study. This list should not be considered all inclusive. Consult individual drug labels for specific information on a compound's propensity to inhibit CYP3A4.

#### **STRONG CYP3A4 INHIBITORS**

atazanavir indinavir nelfinavir ritonavir saquinavir clarithromycin itraconazole ketoconazole

#### **STRONG CYP3A4 INDUCERS**

rifampin carbamazepine phenytoin phenobarbital St. John's wort  
mibefradil nefazodone telithromycin cyclosporin troleandomycin verapamil grape fruit  
seville orange

#### **CYP3A4 SUBSTRATES WITH NARROW THERAPEUTIC INDEX**

alfentanil astemizole cisapride cyclosporine diergotamine ergotamine  
Revised Protocol No.: 01 Date: 30-Sep-2010  
fentanyl pimoziide quinidine sirolimus tacrolimus terfenadine

#### **OTHER CYP3A4 SUBSTRATES, INHIBITORS AND INDUCERS CYP3A4 SUBSTRATES**

**Macrolide antibiotics:** clarithromycin erythromycin NOT azithromycin telithromycin  
**Anti-arrhythmics:** quinidine Benzodiazepines: alprazolam diazepam midazolam triazolam  
**Immune Modulators:** cyclosporine tacrolimus (FK506)  
**HIV Protease Inhibitors:** indinavir ritonavir saquinavir  
**Prokinetic:** cisapride  
**Antihistamines:** astemizole chlorpheniramine  
**Calcium Channel Blockers:** amlodipine diltiazem felodipine  
nifedipine nisoldipine nitrendipine verapamil  
**HMG CoA Reductase Inhibitors:** atorvastatin cerivastatin lovastatin  
NOT pravastatin simvastatin  
**Others:** aripiprazole buspirone gleevec haloperidol (in part) methadone pimoziide  
quinine NOT rosuvastatin sildenafil tamoxifen trazodone vincristine

#### **CYP3A4 INHIBITORS**

amiodarone NOT azithromycin cimetidine

#### **CYP3A4 INDUCERS**

**HIV Antivirals:** efavirenz nevirapine  
diltiazem erythromycin fluvoxamine  
**Others:** barbiturates glucocorticoids modafinil troglitazone rifabutin

## APPENDIX 3 – RECIST 1.1 CRITERIA

### RECIST 1.1 CRITERIA

- Only patients with measurable disease at baseline should be included in protocols where objective tumor response is the primary endpoint.
  - *Measurable disease*: the presence of at least one measurable lesion. If the measurable disease is restricted to a solitary lesion, its neoplastic nature should be confirmed by cytology/histology.
  - *Measurable lesions*: lesions that can be accurately measured in 2 perpendicular diameters with at least one diameter  $\geq 20$  mm using conventional techniques or  $\geq 10$  mm with spiral CT scan using a 5 mm contiguous reconstruction algorithm.
  - *Non-measurable lesions*: all other lesions, including small lesions (longest diameter  $< 20$  mm with conventional techniques or  $< 10$  mm with spiral CT scan), i.e., bone lesions, leptomeningeal disease, ascites, pleural/pericardial effusion, inflammatory breast disease, lymphangitis cutis/pulmonitis, cystic lesions, and also abdominal masses that are not confirmed and followed by imaging techniques.
- All measurements should be taken and recorded in metric notation, using a ruler or calipers. *All lesion measurements must be recorded in millimetres (or decimal fractions of centimetres).*
- All baseline evaluations should be performed as closely as possible to the beginning of treatment and never more than approximately 30 days before the beginning of the treatment.
- The same method of assessment and the same technique should be used to characterize each identified and reported lesion at baseline and during follow-up.
- Clinical lesions will only be considered measurable when they are superficial (e.g., skin nodules and palpable lymph nodes). For the case of skin lesions, documentation by color photography, including a ruler to estimate the size of the lesion, is recommended.

#### Methods of measurement

- CT and MRI are the best currently available and reproducible methods to measure index lesions selected for response assessment. Conventional CT and MRI should be performed with cuts of 10 mm or less in slice thickness contiguously. Spiral CT should be performed using a 5 mm contiguous reconstruction algorithm. This applies to tumors of the chest, abdomen and pelvis. Head and neck tumors and those of extremities usually require specific protocols.
- The utilization of endoscopy and laparoscopy for objective tumor evaluation has not yet been fully and widely validated. Their uses in this specific context require sophisticated equipment and a high level of expertise that may only be available in some centers. Therefore, the utilization of such techniques for objective tumor response should be restricted to validation purposes in specialized centers. However, such techniques can be useful in confirming complete pathological response when biopsies are obtained.
- Tumor markers alone cannot be used to assess response. If markers are initially above the upper normal limit, they must normalize for a patient to be considered in complete clinical response when all lesions have disappeared.
- Cytology and histology can be used to differentiate between PR and CR in rare cases (e.g., after treatment to differentiate between residual benign lesions and residual malignant lesions in tumor types such as germ cell tumors).

#### Baseline documentation of “index” and “non-index” lesions

- All measurable lesions up to a maximum of five lesions per organ and 10 lesions in total, representative of all involved organs should be identified as **index lesions** and recorded

and measured at baseline.

- Index lesions should be selected on the basis of their size (lesions with the longest diameter and perpendicular diameter) and their suitability for accurate repeated measurements (either by imaging techniques or clinically).
- A sum of the longest diameters for *all index lesions* will be calculated and reported as the baseline sum. The baseline sum will be used as reference by which to characterize the objective tumor.
- All other lesions (or sites of disease) should be identified as **non-index lesions** and should also be recorded at baseline. Measurements of these lesions are not required, but the presence or absence of each should be noted throughout follow-up.

### **Evaluation of best overall response**

The best overall response is the best response recorded from the start of the treatment until disease progression/recurrence (taking as reference for PD the smallest measurements recorded since the treatment started). In general, the patient's best response assignment will depend of the achievement of both measurements and confirmation criteria.

Patients with a global deterioration of health status requiring discontinuation of treatment without objective evidence of disease progression at that time should be classified as having "symptomatic deterioration". Every effort should be made to document the objective progression even after discontinuation of treatment.

- In some circumstances it may be difficult to distinguish residual disease from normal tissue. When the evaluation of complete response depends on this determination, it is recommended that the residual lesion be investigated (fine needle aspirate/biopsy) to confirm the complete response status.

### **Confirmation**

- The main goal of confirmation of objective response is to avoid overestimating the response rate observed. In cases where confirmation of response is not feasible, it should be made clear when reporting the outcome of such studies that the responses are not confirmed.
- To be assigned a status of PR or CR, changes in tumor measurements must be confirmed by repeat assessments that should be performed no less than 4 weeks after the criteria for response are first met. Longer intervals as determined by the study protocol may also be appropriate.
- In the case of SD, follow-up measurements must have met the SD criteria at least once after study entry at a minimum interval (in general, not less than 6-8 weeks) that is defined in the study protocol.

## **APPENDIX 4 – IMMUNE RELATED RESPONSE CRITERIA**

### **Immune Related Response Criteria**

#### **4.1 Tumor Assessments**

The immune-related Response Criteria (irRC) is a further refinement of the mWHO criteria to better capture tumor responses in subjects on immunotherapy. The irRC was developed/implemented to address the difference in the natural history of the clinical responses observed in subjects treated with immunotherapy agents which differs from those seen in subjects on other classes of anti-cancer agents.

Differences of response patterns between cytotoxic and immune therapies are now recognized by the scientific community as well as by Regulatory Authorities. These differences have been characterized by Wolchok et al after a post hoc analysis of the radiological responses that were observed during the Phase 2 studies performed in melanoma:

- The appearance of measurable antitumor activity may take longer for immune therapies than for cytotoxic therapies;
- Responses to immune therapies may occur after conventional PD;
- Discontinuation of immune therapy may not be appropriate in some cases, unless PD is confirmed (as is usually done for response);
- Allowance for “clinically insignificant” PD (eg, small new lesions in the presence of other responsive lesions) is recommended;
- Durable SD may represent antitumor activity.

These observations lead to the development of immune-related Response Criteria extensively described by Wolchok et al, used to define efficacy endpoints in more recent ipilimumab studies.

#### **4.2 Radiological Assessment of Tumor Lesions**

##### **4.2.1 CT/MRI**

CT/MRI imaging of the chest and abdomen is required at Screening and at each tumor assessment (TA), regardless of the location of known metastases. In addition, CT/MRI scans must be obtained of anatomic regions not covered by the chest and abdomen scans in subjects where there is clinical suspicion of deep soft tissue metastases (eg, lesions in the thigh). Such additional CT/MRIs will be required at Screening only when deep soft tissue disease is known/suspected and must be consistently repeated at all TAs if a deep soft tissue lesion is identified during Screening. The same imaging modality must be used at all TAs.

Brain scans are required at Screening to rule out CNS metastases. Brain scans to be repeated as clinically indicated. Contrast enhanced CTs are preferred, MRIs are a second choice. Similar methods of TA and similar techniques must be used to characterize each identified and reported lesion at Screening and all subsequent tumor assessments. Imaging-based evaluation is preferred to clinical examination. Helical (spiral) CT scans of the chest and abdomen are preferred. If not available, conventional (non helical, non- spiral CT) should be used; however, a measurable lesion must not have the longest diameter smaller than 20 mm. IV contrast should be used for all CT scans; if IV contrast is contraindicated, oral contrast maybe used, or MRI should be used at the Screening exam and at all TA time points. Subjects who develop contrast allergy after study enrollment must be followed by MRI for subsequent tumor measurements.

A reference measurement ruler must be printed on every image for scale determination. Sections should be contiguous, similarly sized and consistent from visit-to-visit. Section thickness must be based on institutional standards (e.g, from 5 to 8 mm, 10 mm cuts are not recommended). Chest x-rays and ultrasound are not acceptable methods to measure disease.

#### **4.2.2 Bone Scans**

Assessment of irPD is never based only on a new lesion(s) found on bone scans. However, if bone lesions are identified at any time during the study, additional imaging studies of the lesion(s) must be performed to confirm the malignant nature of the new findings on the bone scan. If an abnormal bone scan was observed at any time point throughout the study, a new bone scan must be performed prior to the confirmation of a complete response (eg, the remaining metastatic lesions must have resolved). In case of new lesions such as pleural effusion, cytology must be performed to identify and confirm malignancy. Skin and soft tissue lesions will be captured as non-measurable lesions through physical examination only.

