**5.4 Efficacy Assessments**

In this study, immune-related Response Criteria (irRC; see Appendix 4) will be used to assess subject response to study treatment and guide clinical care. However, response- based assessments in this study will be captured using both modified irRC and RECIST 1.1. The investigator will determine the irRC response at each tumor assessment. The RECIST 1.1 response for the patient will be calculated from the tumor assessment data by the Sponsor and will be used for reporting purposes. The RECIST 1.1 criteria will be used to determine subjects’ best overall response (BOR), and for statistical analysis of efficacy in this study. Assessments of tumor status will be made during screening and then at 6 and 12 weeks and then every 12 weeks thereafter. The irRC represent modifications of the modified WHO criteria reflecting the clinical experience with ipilimumab in the completed and/or ongoing clinical studies in which objective and durable responses (as per mWHO) were observed in subjects following progression and without intervening alternative anti-cancer therapy. As such, the irRC are designed to capture clinical activity of ipilimumab immunotherapy that may not be adequately addressed by the RECIST 1.1 criteria and will only be used for patient management decisions, not formal efficacy reporting.

[REDACTED]

[REDACTED]

[REDACTED]

[REDACTED]

[REDACTED]

[REDACTED]

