### **4.4 Definition of Index / Non-Index Lesions**

Measurable lesions, up to a maximum of **five lesions per organ and ten lesions in total**, must be identified as *index* lesions to be measured and recorded on the CRF at Screening. The *index* lesions should be representative of all involved organs. In addition, *index* lesions must be selected based on their size (eg, lesions with the longest diameters), their suitability for accurate repeat assessment by imaging techniques, and how representative they are of the subject's tumor burden. At Screening, a Sum of the Products of Diameters (SPD) for all *index* lesions will be calculated and considered the baseline SPD. The baseline sum will be used as the reference point to determine the objective tumor response of the *index* lesions at TA.

Measurable lesions, other than *index* lesions, and all sites of non-measurable disease, will be identified as *non-index* lesions. *Non-index* lesions will be recorded on the CRF and will be evaluated at the same assessment time points as the *index* lesions. In subsequent assessments, *non-index* lesions will be recorded as complete response, stable or progression.

All measurable and non-measurable lesions should be assessed at Screening and at the defined TA time points. Extra assessments may be performed, as clinically indicated, if there is a suspicion of progression. The Investigator will base response to treatment using the irRC.

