### **4.6.3 Impact of New Lesions on irRC**

New lesions alone do not qualify as progressive disease. However their contribution to total tumor burden is included in the SPD which in turn feeds into the irRC for tumor response. Therefore, new non-measurable lesions will not discontinue any subject from the study. Definition of Best Overall Response using irRC (irBOR) will be based on the following criteria:

- Immune-related Complete Response (irCR): Complete disappearance of all tumor lesions (index and non-index together with no new measurable/unmeasurable lesions) for at least 4 weeks from the date of documentation of irCR.
- Immune-related Partial Response (irPR): The sum of the products of the two largest perpendicular diameters of all index lesions is measured and captured as the SPD baseline. At each subsequent TA, the sum of the products of the two largest perpendicular diameters of all index lesions and of new measurable lesions are added together to provide the Immune Response Sum of the Product of the Diameters (irSPD). A decrease, relative to baseline of

the irSPD of 50% or greater is considered an irPR. This must be confirmed no less than 4 weeks from the first irPR.

- Immune-related Stable Disease (irSD): irSD is defined as the failure to meet criteria for immune complete response or immune partial response, in the absence of progressive disease.
- Immune-related Progressive Disease (irPD): It is recommended in difficult cases to confirm PD at the following TA. Any of the following will constitute progressive disease:
  - At least a 25% increase in the SPD of all index lesions and new measurable lesions (irSPD) over the nadir SPD calculated for the index lesions.

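### Appendices 3 and 4 disagree on whether superficial skin lesions are measured, so the RECIST 1.1 sum in subjects who have them depends on which appendix the site follows

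*Combined protocol and SAP*

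**What the plan says.** **Appendix 3 (RECIST 1.1).** "Clinical lesions will only be considered measurable when they are superficial (e.g., skin nodules and palpable lymph nodes"). For skin lesions, "documentation by color photography, including a ruler to estimate the size of the lesion, is recommended". Under baseline documentation, all measurable lesions, up to five per organ and ten in total, become index lesions. They are chosen partly for how well they can be re-measured, whether on imaging or clinically, and their longest diameters are summed.

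**Appendix 4 (irRC).** Section 4.2.2: "Skin and soft tissue lesions will be captured as non-measurable lesions through physical examination only". Section 4.4 chooses index lesions for repeat assessment by imaging, and non-index lesions "will be recorded as complete response, stable or progression". Section 4.2.1 requires CT or MRI where deep soft tissue disease is known or suspected at screening, and these scans "must be consistently repeated at all TAs if a deep soft tissue lesion is identified during Screening".

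**Section 5.4.** The investigator assigns the irRC response at each assessment. "The RECIST 1.1 response for the patient will be calculated from the tumor assessment data by the Sponsor", and that result is used for reporting. The same section says that response-based "assessments in this study will be captured using both modified irRC and RECIST 1.1".

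**Section 3.2.1.** Every subject must have disease measurable on CT and/or MRI at baseline.

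**The concern.** The same skin nodule can be a measured index lesion under one appendix and an unmeasured lesion with only a category under the other. RECIST 1.1 is the criterion for reported efficacy, and the sponsor calculates it after the event from what the site recorded. A site that follows Appendix 4 leaves no diameters for the sponsor to use, and a baseline diameter that was never taken cannot be recreated.

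At stake is the comparability of the RECIST results. Two subjects with the same disease course could get different sums, and so possibly different response or progression calls, only because their superficial lesions were recorded under different appendices.

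**Working it through.** The plan states no figure on this point, so there is none to reproduce. The check has two parts: the rules side by side, then the effect on the RECIST sum.

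**1. Rules side by side for a superficial skin nodule above the size limit**

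| Question | Appendix 3 | Appendix 4 |
|---|---|---|
| Can it be measurable? | Yes, if superficial and large enough | No (Section 4.2.2) |
| How is it assessed? | Clinically; ruler photograph recommended | Physical examination only |
| Can it be an index lesion? | Yes | No |
| What is recorded? | Longest diameter, into the sum | Category only (Section 4.4) |

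Nothing in Section 5.4 or the appendices says that skin diameters are recorded separately for RECIST when Appendix 4 is followed.

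**2. Effect on the RECIST sum in one subject**

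The sizes are assumed, because the documents give none. At baseline there are two skin nodules of 30 mm each and one lung lesion of 12 mm on spiral CT. The nodules clear and the lung lesion grows to 15 mm. Appendix 3 sets the limit at 20 mm with conventional techniques and 10 mm with spiral CT, so all three lesions qualify.

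Formula: change = (later sum - baseline sum) / baseline sum.

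- Nodules measured (Appendix 3): baseline 30 + 30 + 12 = 72 mm; later 0 + 0 + 15 = 15 mm; change (15 - 72)/72 = -79%.
- Nodules not measured (Appendix 4 recording): baseline 12 mm; later 15 mm; change (15 - 12)/12 = +25%.

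Both sums can be calculated, but they have opposite signs.

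**3. A less extreme case**

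Let s be the skin share of the baseline sum. Then change = (1 - s) x change in imaged lesions + s x change in skin lesions. Assume that imaged lesions shrink by 40% and skin lesions do not change.

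- Skin left out: -40%.
- s = 25%: 0.75 x (-40%) + 0.25 x 0 = -30%.
- s = 50%: 0.50 x (-40%) + 0.50 x 0 = -20%.

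**4. How far it could reach**

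The documents do not say how many subjects will have skin or soft tissue lesions. If 10% to 40% did (an assumption), that is 0.10 x 36 = 3.6 to 0.40 x 36 = 14.4, or about 4 to 14 of the planned maximum of 36. This is an upper bound on those affected at that prevalence, because only superficial lesions that meet the size limit and are chosen as index lesions change the sum.

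One reclassified subject moves ORR by 1/36 = 2.8 percentage points if all 36 are evaluable, or by 1/12 = 8.3 points among 12 at the MTD.

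**The case against.** The strongest reply is that each appendix serves its own criterion. Appendix 4 is the irRC appendix, Appendix 3 has its own way to size skin lesions, and Section 5.4 speaks of capture under both criteria. A CRF with separate RECIST fields would hold both classifications without conflict. This stands in part: the CRF is not among the documents, so loss of the diameters is a risk and not a certainty. But the Appendix 4 sentence is not limited to irRC and says how these lesions are to be captured. No text tells a site to measure them for RECIST as well, and the ruler photograph is only recommended.

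A reader might infer three stronger points. The documents support none of them.

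- **That RECIST response and PFS cannot be derived.** Section 3.2.1 requires CT- or MRI-measurable disease in every subject, so each has a baseline sum without skin lesions. Progression can still be read from imaged lesions, non-index lesions and death.
- **That RECIST and irRC contradict each other.** In the constructed subject, if the lung lesion is 12 x 12 mm and then 15 x 15 mm, the irSPD goes from 144 to 225 mm2, or +56%, against -79% for the RECIST sum. These are different criteria and may legitimately differ. The relevant comparison is RECIST with and without the nodules.
- **That the skin rule is what keeps skin growth out of irPD.** In Appendix 4, Section 4.6.3, the irPD criterion given counts index and new measurable lesions, so growth in any non-index lesion is treated the same way. The statement that "new non-measurable lesions will not discontinue any subject from the study" concerns new lesions, not growth of baseline skin lesions.

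On soft tissue, Section 4.2.2 of Appendix 4 can be read as meaning superficial lesions only, which would fit the imaging rule in Section 4.2.1. The word is missing, so this is a gap in wording more than a deep conflict.

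**Conclusion.** The appendices conflict on superficial skin lesions, and nothing in Section 5.4 resolves it. In subjects with qualifying superficial lesions, the RECIST sum depends on which appendix the site followed, and ORR, DCR and PFS can follow from it. The difference can be large in one subject (-79% against +25% in the constructed case) or moderate (-40% against -30% or -20%). Appendix 3 as written gives no percentage thresholds for partial response or progression, so these examples show a change in the sum, not a documented change of category.

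The conclusion assumes that the CRF follows Appendix 4 and has no separate RECIST field for skin diameters. The number of subjects affected is unknown. Anti-tumor activity is a secondary, descriptive objective, and the MTD rests on DLTs and is not touched. The point should be corrected because the correction is cheap and the missing data could not be recovered.

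**What to change.** 1. State in Section 5.4 and on the CRF that superficial lesions meeting the Appendix 3 size limit have their longest diameter recorded at baseline and at each assessment, supported by the ruler photograph that Appendix 3 already recommends, and that they enter the RECIST sum under its index-lesion rules. Name the size limit that applies to clinical measurement.
2. Limit the skin and soft tissue sentence in Appendix 4, Section 4.2.2, to irRC.
3. Reconcile Sections 4.2.1 and 4.2.2 of Appendix 4, so that it is clear which soft tissue lesions are imaged and which are assessed by physical examination.

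Whether skin lesions should count toward irSPD and irPD is a separate matter. Section 4.3.4 ties treatment duration to progression by irRC, so that question is for the sponsor to reconcile, and no rule is proposed here.

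The cost is a few sentences and a CRF field, with slightly more lesion recording at each assessment. It needs to be in place before baseline measurements are taken.
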